3.6.2 Procedures at Care Sites

Participating HIV care sites will serve as the comprehensive 'medical home' for coordination of all HIV-positive patient care needs, including substance use, mental health, and other support services.

As newly diagnosed HIV-positive patients present for care, care sites will evaluate CD4 cell count and VL. Care sites will then create an appropriate medical plan for each patient, consistent with current HIV care and treatment guidelines. Simultaneously, care

sites will also assess patients and link them as appropriate to support services. Finally, valid coupons distributed by HIV test sites will be redeemed with FI gift cards.

Prior to study implementation, all HIV care site staff will be trained on the procedures for the FI intervention, ART initiation according to current guidelines, and the importance of linking HIV-positive patients to appropriate support services. In addition, as part of study orientation and training for HIV care providers, existing support service linkages will be reviewed.

To collect clinic-level information on services available to patients in the two jurisdictions, HIV care sites will be surveyed at baseline and annually thereafter to ascertain support services available on- and off-site (e.g., social services, substance use treatment, support groups, mental health resources, etc). The study team will develop and maintain a comprehensive list of support services in the two intervention communities. In addition, the study will regularly update lists for care sites of contact persons and referral processes at support service agencies.

Because the study will use surveillance data to measure outcomes and will not collect data on individual patients, the study will not be able to document or track linkages to ancillary services in the Linkage-to-care and Viral Suppression study components. Information on referrals made and completed by patients is not part of the surveillance data that will be analyzed for study outcomes. Likewise, offering FIs for completion of linkages to drug treatment or mental health services is not possible, as it would also require following individual patients with explicit data collection. However, for the subset of patients completing Patient Survey, we will collect data on the frequency of use, ease of access, and patient experiences with support services (including mental health, drug abuse, case management, etc).

3.6.3 Monitoring HIV Test Sites

It is possible that members of the intervention communities will learn of the FI to strengthen linkage-to-care and seek out HIV test sites offering these incentives. In all likelihood, the majority of individuals who seek testing will not know their HIV status yet and, thus, will be unaware that incentives are being offered for linkage-to-care. In addition, many of the HIV test sites in the study (~seven out of the 20 participating HIV test sites in each city) will be hospitals in which HIV testing will take place in emergency departments and inpatient units. Individuals seen in these settings are usually not there for the purpose of obtaining an HIV test. Thus, it is unlikely that these individuals will seek medical services based on the availability of FIs for linkage to HIV care.

However, it is possible that some individuals, who are aware of their HIV infection, may "recycle" through the HIV test sites due to the availability of FIs. There are some natural barriers to this phenomenon, as it is likely that the staff at these HIV test sites will recognize individuals who are testing with undue frequency. In these cases, staff may withhold the FI coupons from those who have already received them for a prior HIV-positive test. Another natural barrier is that individuals are known at HIV care sites, so individuals will be unable to re-link repeatedly to the same HIV care site. In addition, the FI intervention is designed such that multiple activities (lab-work and provider

interaction, both of which take time and effort) are required for the full redemption, which may discourage some from repeated linkage.

It should also be noted that based on the HIV prevalence in the intervention cities, relatively few people test positive out of all of those who test. Thus, the number of people who could "recycle" through the HIV test sites is relatively small compared to the total testing done in these venues.

Despite all of the barriers to HIV-test-site migration and linkage recycling, FI may encourage these phenomena; thus, the study team will use surveillance data to monitor these potential situations. Specifically, the team will monitor the number of duplicate linkage-to-care events in the name/ID-based surveillance data system over time. So, for example, in the case where a person re-tests at five unique HIV test sites (all offering linkage-to-care incentives) and links to five unique participating HIV care sites over the course of six months, HIV surveillance data will capture this event.

In addition, the team will monitor whether the number of positive HIV tests becomes severely disproportionately distributed among the participating HIV test sites (a sign that HIV testing is much reduced or increased at some sites). This information will be examined in an on-going fashion, and if site migration or linkage recycling becomes highly extensive so that it becomes a burden on HIV test or care sites, or threatens the validity of the evaluation, this component of the study will be re-evaluated. Such reevaluation may include discussions with the community advisory group to design other mechanisms to minimize such migration, or, if needed, a redesign of this component of the study may be embarked on by the study team.

3.7 Study Duration for Linkage-to-Care

The duration of the FI intervention for the Linkage-to-Care component of the study is depicted in Figure 2. Coupons will be available at the HIV test sites randomized to the FI arm for 21 months. These coupons can be redeemed after the initial visit with an HIV provider at HIV care sites for a total of 24 months (for the entire time coupons are distributed at certain HIV test sites plus an additional three months).

Figure 2: Duration of FI Intervention for Linkage-to-Care

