3.2 Design for Linkage-to-Care

The Linkage-to-Care component of the study is a two-arm, site-randomized, prospective, effectiveness clinical trial conducted within each intervention community. This study component compares the effectiveness of an FI intervention to link HIV-positive individuals from HIV test sites to HIV care sites with the usual SOC procedures. Each HIV test site will be randomized to either the intervention or SOC arm of the study. For this component of the study, study outcomes will be evaluated through routinely reported HIV surveillance data. Using surveillance data, study outcomes will continue to be evaluated for a period of one year after the FI intervention ends.

In order to identify the SOC for linkage, against which the incentives intervention will be assessed, an appropriate facility administrator will complete a brief survey that will collect key attributes of HIV testing sites, including types of navigation and support services already available to patients to facilitate linkage-to-care. Data will be collected from sites annually from 2009 - 2013.

For the purposes of this protocol, we consider an HIV-positive individual linked to care when that person has a VL or CD4 cell count assessment at an HIV care site within 3 months of confirmatory WB testing.

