3.8.2 Sample Size and Power

The primary endpoint of this study component is proportion of cases (newly diagnosed and previously diagnosed but not in care) with a CD4 cell count and/or VL measurement within three months of the diagnostic WB.

Randomization is by testing site, with balance achieved for baseline volume of testing and baseline linkage-to-care rates. Accrual of participants into the Linkage-to-Care

component of the study will occur over the first 24 months of the study, when eligible persons receive the FI coupon at an HIV test site randomized to the FI arm of the study. There will be no follow-up for this component of the study, other than the two visits in care (or a combined lab/provider intake visit).

In 2007, in the 20 testing sites with the highest volume in the Bronx, NY, 611 newly diagnosed HIV-infected people were identified. Of those, 77% were liked to care within three months, with linkage at different testing sites ranging from 30% to 100%. The mean number of newly diagnosed cases per provider in 2008 was 31, and ranged from five to 93. The intra-class correlation (ICC) of proportion linked to care in the Bronx was 0.27.

In 2008, in the 20 testing sites in Washington, D.C, the jurisdiction with the highest volume of people testing HIV-positive, 783 newly infected cases were identified. Of these, 67% were linked to care, ranging across different testing sites from 5% to 100%. The mean number of newly diagnosed cases per provider in 2008 was 40, and ranged from eight to 143. The ICC of proportion linked was 0.31.

These estimates do not include the population of those re-linking to care. It is anticipated that linkage success in SOC for this population will be lower because of the history of loss to care. We could reasonably expect that: 1) the number of people eligible for linkage-to-care will be higher because of longer study duration and addition of re-linked to care cases; 2) the proportion linked to care will be lower because of the re-linked to care cases; and, therefore, 3) the ICC will be smaller. It is assumed that the number of cases to be linked to care during the 24-month study duration will be similar to these past case loads on an annual basis. We will randomize 20 testing sites in each intervention city, and we expect to identify between 1200 and 2400 individuals for linkage-to-care, a mean of 60-120 people per testing site.

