Table 2 below gives the mean number of linkage cases needed per testing site to detect an increase in linkage-to-care given 20 sites per arm (*i.e.* 40 in all). With a mean ranging from 80 to 100 linkages per site during the 24 months of the study, we would have 80% power, even with a high ICC, to detect a 13% change in proportion linked to care. If higher numbers are eligible for intervention due to linkage-to-care (*e.g.* 140), we would attain 90% power to detect this magnitude of difference. Note that the ICC coefficient estimated from the linkage-to-care of newly detected cases is high in large part because of sites with a small number of newly detected cases and 100% success in linking to care. It is probable that the ICC observed in the trial will be lower.

This sample size calculation for clustered designs uses the approach described by Thomson, Hayes and Cousens (Hayes and Bennett 1999; Thomson, Hayes et al. 2009).

 Table 2.
 Mean number at each site required to achieve sufficient power to detect differences in proportion of newly detected or reconnected to care within three months of testing. Number of clusters fixed at 20 per arm

Mean percentage linked to care at a site		Standard deviation can	-	Intra-class	Mean number of potential cases for linkage-to-care per testing site	
Standard of care	Intervention	Standard of care	Intervention	correlation	80% power	90% power
67%	80%	17%	12%	0.127	37	49
67%	80%	20%	15%	0.183	54	72
67%	80%	26%	19%	0.309	102	137
67%	75%	17%	14%	0.127	105	140
67%	75%	20%	17%	0.183	152	203
67%	75%	26%	22%	0.309	287	384

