3.8.4.1 Primary Effectiveness Analysis

The population for assessment of Linkage-to-Care is the following:

- 1. All individuals with newly detected HIV infections reported to the HIV surveillance system for the DOH jurisdiction of Washington, D.C. and the Bronx, NY who were tested at any of the 40 testing sites in the study
- 2. All participants eligible for re-linkage to care, defined as a WB recorded in the enhanced HIV/AIDS Reporting System (eHARs), at any of the 40 testing sites in the study after the implementation of FIs, who had no VL or CD4 assessment by a provider in the previous 12 months

The endpoint is the percentage of participants with a VL or CD4 cell count assessment within three months of the WB confirmation (separate from clinical assessment done at the time of the confirmation visit). Participants in the FI arm are attributed to the linkage-to-care strategy in place at the site where the first HIV-positive result was detected.

The estimation of intervention effect will test for a change in odds ratio of linkage-to-care between the SOC and FI test sites, assuming a correlation within participants tested at the same site, using Generalized Estimating Equations (GEE) methods.

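### Coupons are issued for 21 months, but linkage accrual and power run on 24 and the primary population has no closing date, so FI-site cases with no coupon on offer can enter the primary comparison

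*Protocol*

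**What the plan says.** Four parts of the protocol bear on the window for the Linkage-to-Care component.

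- **Section 3.7 (duration).** "Coupons will be available at the HIV test sites randomized to the FI arm for 21 months". Redemption at care sites runs "for a total of 24 months (for the entire time coupons are distributed at certain HIV test sites plus an additional three months". This agrees with Section 3.5, which gives each coupon a three-month life.
- **Section 3.8.2 (sample size).** Accrual into this "component of the study will occur over the first 24 months of the study, when eligible persons receive the FI coupon". Power rests on the same 24 months: "With a mean ranging from 80 to 100 linkages per site during the 24 months of the study, we would have 80% power" for a 13-point difference, with "Number of clusters fixed at 20 per arm".
- **Section 3.8.4.1 (primary analysis).** The first population group is "All individuals with newly detected HIV infections reported to the HIV surveillance system" who were tested at the 40 study sites, with no dates given. The second group, those eligible for re-linkage, has a start (after FIs are implemented) but no end. FI-arm cases are attributed by the strategy at the testing site, not by receipt of a coupon.
- **Section 3.2 (design).** Using surveillance data, "study outcomes will continue to be evaluated for a period of one year after the FI intervention ends", so later cases will be in the extract.

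Section 3.8.4 says that the approach for the primary comparison is described in the protocol and sends only the secondary endpoints to the statistical analysis plan.

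**The concern.** Sections 3.7 and 3.8.2 cannot both be right about how long coupons are handed out. Redemption does not explain the gap, because the accrual sentence in Section 3.8.2 speaks of receiving the coupon at the test site, not of redeeming it at the care site.

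The conflict matters because nothing in Section 3.8.4.1 closes the population at the end of coupon issue. If accrual follows Section 3.8.2 and coupons follow Section 3.7, the last three months contribute FI-site cases who had no access to the intervention. They would pull the odds ratio towards 1. The attribution rule does not settle it. After month 21, the strategy in place could mean the randomised arm, which dilutes the effect, or what the site is then doing, which departs from the randomised assignment. Leaving this open also leaves a choice that could be made once outcome data are visible.

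**Working it through.** **Inputs.** Coupon issue 21 months (3.7). Accrual 24 months (3.8.2). Linkage 67% against 80%, or 67% against 75%, with 20 sites per arm and stated power of 80% and 90% (3.8.2, Table 2). Two-sided alpha of 0.05 is an assumption, because none is stated for this component; z values are then 1.960, 0.842 (80% power) and 1.282 (90% power).

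**The plan's own figure.** Table 2 does not reproduce with the usual unmatched cluster formula, c = 1 + (zα + zβ)² [p0(1−p0)/m + p1(1−p1)/m + SD0² + SD1²] / (p1−p0)². In the high-ICC row (SD 26% and 19%) with unlimited cases per site, the standard error is √[(0.0676 + 0.0361)/19] = 0.0739. Power then cannot exceed Φ(0.13/0.0739 − 1.960) = about 42%. That is a separate matter. Below, the stated power is taken at face value, so this point does not depend on it.

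**Share of FI cases with no coupon on offer.** With even accrual, f = (24 − 21)/24 = 12.5%.

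**Diluted effect**, with no carry-over after coupons stop: effect × (1 − f).
- 13 × 0.875 = 11.4 points; 8 × 0.875 = 7.0 points.
- On the odds-ratio scale of the primary analysis: (0.80/0.20)/(0.67/0.33) = 1.97 becomes (0.784/0.216)/(0.67/0.33) = 1.79.

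**Power** = Φ[(1 − f)(zα + zβ) − zα].
- Stated 80%: Φ(0.875 × 2.802 − 1.960) = Φ(0.491) = about 69%.
- Stated 90%: Φ(0.875 × 3.242 − 1.960) = Φ(0.876) = about 81%.

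**Closing the population at 21 months instead.** The effect stays at 13 points, and 80 to 100 cases per site becomes 80 × 0.875 = 70 to 100 × 0.875 = 87.5.
- In the Table 2 row with the smallest between-site SDs (17% and 12%), between-site variance is 0.0289 + 0.0144 = 0.0433. The within-site part is (0.2211 + 0.1600)/m, which is 0.0048 at m = 80 and 0.0054 at m = 70. The total rises from 0.0481 to 0.0487, so the standard error rises by about 0.7%. A stated 80% becomes Φ(2.802/1.007 − 1.960) = about 79%.
- A harsher bound lets information depend on case numbers alone. Table 2 appears to scale that way: 137/102 = 1.34, and (3.242/2.802)² = 1.34. Then 80% becomes Φ(2.802 × √0.875 − 1.960) = about 75%.

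Either way, closing at 21 months costs less than keeping cases who had no coupon on offer (69%).

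**The case against.** The best defence is that the 24 months in Section 3.8.2 is loose shorthand for 21 months of issue plus three of redemption. Some of the wording fits this. The case-load assumption counts people linked within the period ("It is assumed that the number of cases to be linked to care during the 24-month study duration will be similar to these past case"), and the power sentence counts linkages, which can fall up to three months after a month-21 diagnosis. The accrual sentence also ties accrual to receiving a coupon, so months without coupons fall outside its own description. This stands in part: the protocol does not say in terms that FI-site cases from months 22 to 24 are to be analysed, and dilution is what the text permits, not a declared plan. But the accrual sentence gives 24 months for receipt of coupons, and Table 2 counts potential cases for linkage, not linkages.

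A second defence is that calendar cut-offs for a surveillance extract are commonly left to the statistical analysis plan. That is fair for exact dates. It does not cure a stated accrual period that contradicts a stated intervention period. For the Viral Suppression component, Section 4.8.4.1 does fix its window in the protocol (months 12 to 24). Figure 2 could not be read here and may show the intended timing.

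Two stronger readings are tempting, and the documents do not support them. A reader might infer from Section 3.2 that the year after incentives end is pooled into the primary analysis, which would dilute the effect far more. Section 3.2 says only that evaluation continues. A reader might also infer from the undated first group that diagnoses made before randomisation count. A study window is plainly implied, even though it is not written.

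**Conclusion.** The point holds as a contradiction with a conditional consequence. Sections 3.7 and 3.8.2 disagree by three months on how long coupons are issued, and Section 3.8.4.1 does not close the population, so cases with no coupon on offer can enter the FI arm. If they do, the 13-point effect becomes about 11.4 points, and stated power falls from 80% to about 69%, or from 90% to about 81%.

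These sizes assume even accrual over 24 months, two-sided alpha of 0.05, the stated power at face value, and no carry-over of the incentive's effect after month 21. With full carry-over there would be no dilution, so under even accrual the effect lies between 11.4 and 13 points. The contradiction itself is certain; the dilution depends on how the team applies the text. The documents do not show which of the two durations was intended.

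**What to change.** 1. Reconcile Sections 3.7 and 3.8.2 to a single coupon-issue window, and state the redemption period separately from it.
2. In Section 3.8.4.1, define both population groups, in both arms, by the date of the qualifying positive test (WB confirmation). Use the same opening and closing dates for all sites within a city, tied to coupon availability, and follow each person for three months. State that attribution is by randomised arm throughout that window.
3. Restate expected cases per site and power in Section 3.8.2 for the agreed window. If it is 21 months, 80 to 100 per site becomes about 70 to 88.
4. Report cases after the last coupon-issue date only as a separate post-incentive analysis, which gives the extra year in Section 3.2 a defined place.

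The cost is protocol wording. If 21 months is kept, about 12% of cases per site are lost from the primary analysis. With the between-site SDs in Table 2, that takes a stated 80% power to about 79%, and to about 75% on the harsher bound.

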3.8 Statistics and Data Analysis for Linkage-to-Care

3.8.1 Endpoints

3.8.1.1 Endpoints for the feasibility of using financial incentives in the HIV-positive population for Linkage-to-Care

The feasibility endpoints for the Linkage-to-Care component of the study are the following:

- Number of individuals eligible for incentives (see section 3.3) and number of individuals receiving incentives (upon linkage to HIV care) at participating sites
- Cost of the program including staffing, infrastructure and incentives

3.8.1.2 Endpoints for the Effectiveness of Linkage-to-Care

In this site-randomized design, Linkage-to-Care effectiveness endpoints will be evaluated for each site and intervention effectiveness assessed by comparing site outcomes for intervention vs. SOC sites.

The effectiveness endpoints for the Linkage-to-Care component of the study will be ascertained based on HIV surveillance data and will include the following:

- Proportion of HIV-positive individuals at each testing site, who either have a newly detected HIV infection (based on new surveillance case with confirmed WB) or who were previously diagnosed but were out of care (based on no VL or CD4 ascertainment in the year prior to a repeat WB test in an existing surveillance case), and who presently are linked to care as evidenced by having a CD4 cell count and/or VL measurement at a separate visit within three months of WB confirmation
- Mean time interval at each testing site from HIV diagnosis (WB confirmation) to first CD4 cell count or VL for those with newly detected HIV infection and those who were previously diagnosed but were out of care
- Proportion of HIV-positive individuals at a testing site (overall, and separately for those with newly detected HIV infection and those previously diagnosed who were out of care) with at least two CD4 cell count and VL measurements in the prior year

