In the supplement to HIV/AIDS surveillance (SHAS) project, analyses of interview data collected during 2000-2004 from over 20 U.S. cities, counties, and states, indicated that 72% of persons reported entering HIV care within three months of testing HIV-positive (Reed, Hanson et al. 2009). Barriers associated with failure or delayed entry into HIV care include structural, financial and personal/cultural factors. Such factors include first-time HIV testing and anonymous HIV testing (Reed, Hanson et al. 2009), longer waiting time for initial care appointment (Mugavero, Lin et al. 2007) or being diagnosed at earlier stage of HIV disease when patients report "feeling well" (Tobias, Cunningham et al. 2007). In a NYC study using 2003 HIV surveillance data, Torian et al. found that 64% of patients initiated HIV care within three months of HIV diagnosis, 19% initiated care more than three months after diagnosis, and 17% never initiated care. Delay in initiation of care was associated with HIV testing in a community site, in the correctional system, at a sexually transmitted infection or tuberculosis (TB) clinic, non-white race, injection drug use and foreign birth (Torian, Wiewel et al. 2008).

The national five-year multisite Outreach Initiative funded by Health Resources and Services Administration (HRSA) in 2001 identified a number of effective programmatic interventions for engaging and retaining HIV-positive persons in care, including education and outreach, strengthening of referrals, provision of linkage coordination and navigation services, and case management (Rajabiun, Mallinson et al. 2007; Tobias, Cunningham et al. 2007). For instance, an "HIV system navigation" approach was successful in reducing barriers to establishing care and improved health outcomes in a multisite study over 12-month period (Bradford, Coleman et al. 2007). The CDC-funded Antiretroviral Treatment Access Study (ARTAS) strengths-based case management intervention, delivered at CBOs and health departments in 10 sites across the United States during 2005-2006, resulted in 79% of recently diagnosed HIV-positive persons receiving HIV medical care within six months of enrolling in the study (Gardner, Metsch et al. 2005; Craw, Gardner et al. 2008).

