3.5 Intervention for Linkage-to-Care

At HIV test sites assigned to FIs, individuals permitted to consent for HIV care according to New York State or Washington, D.C. law who test HIV-positive will be provided with a coupon that is redeemable at participating HIV care sites. These coupons will be designed so they will not breach patient confidentiality (for example, there will be no patient names, no indication of HIV status, and no clinic names on these coupons). Patients presenting coupons to participating HIV care sites will be given an FI upon completion of a blood draw/lab visit (\$25), which is usually the first visit, and another FI

(\$100) upon an interaction with their healthcare provider, which is usually at a second visit. Alternatively, for those patients who complete a comprehensive visit at participating care sites, a visit that includes both the lab and provider components for Linkage-to-Care, a \$125 FI gift card will be provided.

The coupons distributed at the HIV test sites must be redeemed at the HIV care sites within three months of the date that a participant receives them.

The proportion of persons successfully linked to care within three months of their HIVpositive test will be compared, through the use of routinely collected HIV surveillance data, between sites implementing the incentives intervention and those with SOC procedures for linkage-to-care.

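### The secondary linkage endpoint, a site mean time to first CD4 or VL, has no value for people who never link, so the direction of its arm comparison is not reliable

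*Protocol*

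**What the plan says.** Section 3.8.1.2 gives three effectiveness endpoints for Linkage-to-Care, with "intervention effectiveness assessed by comparing site outcomes for intervention vs. SOC sites". The second is the "Mean time interval at each testing site from HIV diagnosis (WB confirmation) to first CD4 cell count or VL" and it applies "for those with newly detected HIV infection and those who were previously diagnosed but were out of care". So the named population is everyone eligible, and the summary is a mean at each site.

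For this component the protocol gives no value, maximum time or censoring rule for a person who has no CD4 or VL. Section 3.8.2 names the proportion linked within three months as the primary endpoint, which makes the time interval secondary. Section 3.8.4 leaves the analysis of secondary endpoints to the statistical analysis plan.

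The protocol's own figures show that many people would have no interval, or a long one:

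- Section 1.1.3, on New York City surveillance data from 2003, reports 64% in care within three months and states that "19% initiated care more than three months after diagnosis, and 17% never initiated care".
- Section 3.8.2 gives baseline linkage of 77% in the Bronx and 67% in Washington, D.C., with D.C. sites ranging from 5% to 100%.

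**The concern.** A site mean can be taken only over people who have an interval, that is, over those who linked. Linking happens after randomisation and is what the incentive is designed to increase. If it works, the linked group at FI sites contains people who would not have linked under SOC. The two means then describe differently selected groups, and the protection of randomisation is lost for this endpoint.

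The result can mislead in a simple way. If the added linkers take longer than the average SOC linker, the FI mean goes up even though more people are in care and nobody was delayed. A reader of the results would then see a higher linked proportion beside an apparently slower time to care, with no way to tell selection from a real delay.

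**Working it through.** The protocol states no expected mean, SD or power for this endpoint, so there is no planned figure to reproduce. The check compares the mean among linkers with a measure that counts everyone.

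**Inputs.** Shares of 64%, 19% and 17% are from Section 1.1.3. Coupon validity of three months is from Section 3.5. The linkage proportions of 67% and 80% are from Table 2. The documents give no linkage times, so all times are assumptions: 30 days for early linkers and 180 days for late linkers in the main example.

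**Formulas.**
- Mean among linkers = sum of (share × time) over linkers ÷ total share linked.
- Restricted mean to 12 months = sum of (share × time) over linkers + share never linked × 365.

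**Step 1, SOC.**
- Sum over linkers: 0.64 × 30 + 0.19 × 180 = 19.2 + 34.2 = 53.4.
- Mean among linkers: 53.4 ÷ 0.83 = 64.3 days.
- Restricted mean: 53.4 + 0.17 × 365 = 53.4 + 62.05 = 115.5 days.

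**Step 2, FI moves 10 points from never to day 80** (inside coupon validity; nobody else changes).
- Mean among linkers: (53.4 + 0.10 × 80) ÷ 0.93 = 61.4 ÷ 0.93 = 66.0 days, so FI looks 1.7 days slower.
- Restricted mean: 61.4 + 0.07 × 365 = 61.4 + 25.55 = 87.0 days, so FI is 28.5 days faster.
- Linked within three months: 64% + 10% = 74%.

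**Step 3, other patterns.** Each moves 13 points, the size of effect used in Table 2.

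| FI effect | Mean among linkers | Against 64.3 |
|---|---|---|
| Late to day 30 | (0.77 × 30 + 0.06 × 180) ÷ 0.83 = 40.8 | faster |
| Never to day 30 | (53.4 + 3.9) ÷ 0.96 = 59.7 | faster |
| Never to day 60 | (53.4 + 7.8) ÷ 0.96 = 63.8 | about equal |
| Never to day 90 | (53.4 + 11.7) ÷ 0.96 = 67.8 | slower by 3.5 days |

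When the incentive only converts never-linkers, the mean among linkers rises exactly when the added people link later than the SOC linkers' mean, here 64.3 days.

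**Step 4, sensitivity to the assumed times.** With early means of 0.75 to 1.5 months and late means of 4.5 to 12 months, that threshold runs from 1.6 to 3.9 months. It lies inside three months for most of these combinations. It exceeds three months when late linkers are assumed very slow, and then converted never-linkers who arrive within coupon validity do not reverse the sign.

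**Step 5, a three-month horizon with Table 2's 67% and 80%.** Assume that SOC linkers average 1.0 month and that the extra 13% link at 2.5 months.
- Mean among linkers: 1.00 against (0.67 × 1.0 + 0.13 × 2.5) ÷ 0.80 = 0.995 ÷ 0.80 = 1.24 months, so FI looks slower.
- Restricted mean: 0.67 + 0.33 × 3 = 1.66 against 0.995 + 0.20 × 3 = 1.60 months, so FI is faster.

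With the SOC mean at 0.75 to 1.5 months and the extra linkers at 2.0 to 2.5 months, the mean among linkers rises by 0.08 to 0.28 months, while the restricted mean falls by 0.07 to 0.13. If the extra linkers arrive at 0.5 months, the mean among linkers falls by 0.04 to 0.16.

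**Step 6, site level.** At the D.C. average of 40 cases per site, 5% linkage would leave 0.05 × 40 = 2 people to define that site's mean. The protocol does not say how large the 5% site is, so this is only an illustration.

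**The case against.** The strongest reply has three parts.

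First, the text does not exclude never-linkers. It names all eligible people, the endpoint is secondary, and its analysis is left to a statistical analysis plan that is not at hand. A restricted mean over all eligible people would be one way to estimate a mean interval in that population. This stands in part: the restriction to linkers is a consequence of the wording, not something the protocol says. But what Section 3.8.1.2 fixes is a site mean of an interval that does not exist for non-linkers. The protocol does not leave the parallel problem in Viral Suppression wholly to the plan: Section 4.8.1.2 states the principle for missing VL results there and censors people who move away. Linkage timing has no counterpart.

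Second, a reader might infer that the incentive would draw people in very late, for instance at 180 days, and so produce a large reversal. The documents do not support that. Coupons "must be redeemed at the HIV care sites within three months of the date that a participant receives them", so linkage caused by the coupon should fall mostly inside that window. Late arrivals would also leave the primary endpoint unchanged, so there would be no primary benefit for the mean to contradict. Reversals inside the window are smaller: 1.7 and 3.5 days in Steps 2 and 3.

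Third, a reader might infer that the endpoint is biased against the incentive. That is not shown either. Bringing late linkers forward, or adding fast ones, makes FI look faster. The direction depends on linking times that the documents do not give.

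**Conclusion.** The point holds for a secondary endpoint. Computed as written, the mean time to first CD4 or VL compares groups selected on the outcome under study, and its sign is not reliable. In the main example it worsens from 64.3 to 66.0 days, while linkage within three months improves from 64% to 74% and the 12-month restricted mean improves from 115.5 to 87.0 days. These figures rest on the 2003 New York City shares and on assumed times of 30, 80 and 180 days. Other plausible times give a larger reversal, none, or the opposite sign.

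A reader might extend this to the trial's main linkage conclusion. The documents do not support that. The primary endpoint counts everyone who fails to link, and the sizing "to detect a 13% change in proportion linked to care" and the GEE analysis do not use the time interval. The protocol should be changed, but the point does not threaten the primary result.

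**What to change.** Reword the second endpoint in Section 3.8.1.2 as time from WB confirmation to first CD4 or VL in all eligible people, with those who have not linked censored at the end of surveillance follow-up. Summarise it by the restricted mean time to a stated horizon, or by the cumulative incidence of linkage, with standard errors that allow for clustering by testing site.

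Twelve months is a workable horizon. Section 3.2 continues surveillance outcomes for a year after the incentive ends, and Section 3.7 stops coupon distribution at month 21. The last coupon recipient therefore has at least 12 months, or 15 if the incentive is taken to end with redemption at month 24. Section 3.8.2, however, says that this component has no follow-up beyond the care visits and describes accrual over 24 months. These statements must be reconciled before the horizon is fixed.

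The cost is a change of endpoint wording and a standard time-to-event analysis. It uses the same surveillance dates and needs no new data.
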